3.3.2 Follow-up for withdrawn subjects

If participants are withdrawn from the study for any of the reasons noted above prior to randomization, they will be replaced until a total of 240 participants have been randomized to the study. Subjects who withdraw themselves or are withdrawn from the study at a visit will be asked to complete the study visit including a questionnaire regarding the reasons for dropping out.

For participants who withdraw themselves from the study, they will be asked if we can follow up with them at the week 16 visit. We will contact them via one call, message, and letter to complete the week 16 visit. If they wish not to be contacted to complete the week 16 visit, they will not be contacted.

If participants are lost to follow-up (i.e. simply do not respond to calls or letters without formally withdrawing) one final attempt will be made to contact them for the week 16 visit via one call, message and letter. If they complete the week 16 visit they will also be invited to the final (week 20) visit.

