NIDA Drug Use (36)	X							X
AUDIT-C(37, 38)	X							X
Environmental tobacco smoke questionnaire (39)		X						
Cigarette Perceived Health Risk		X	X		X			X
Nicotine dependence (FTND, HONC, PSCDI (31, 40, 41))	X	X		X	X	X	X	X
Nicotine Use Disorder	X							X
PROMIS Dependence	X							X
Minnesota Nicotine Withdrawal Scale (42)	X	X		X	X	X	X	X
Questionnaire of Smoking Urges (QSU) (43, 44)	X	X		X	X	X	X	
Confidence to Quit							X	X
Mental Health and Wellbeing								
MINI International Neuropsychiatric Interview (MINI) (34)	X							
Kessler K6 scale (45, 46)		X	X		X	X	X	X
CES-D, QIDS (depression) (47) (48)		X	X		X	X	X	X
Overall Anxiety Severity Impairment Scale (OASIS) (49)		X	X		X			X
Perceived Stress Scale (50)		X	X		X			X
Positive and Negative Syndrome Scale (PANSS-6) (51)		X	X		X	X	X	X
Clinical COPD questionnaire (CCQ) (52)		X	X		X	X	X	X
PROMIS Sleep Disturbance Short Form (53)		X	X		X			X
INTERHEART and WI-PREPARE (55, 56)	X							
Biomeasures								
Weight (57)		X	X		X	X	X	X
Height		X						
Waist and hip circumference (57)		X						X
Blood Pressure, Pulse (58, 59)	X	X	X		X	X	X	X
Exhaled CO	X	X	X		X	X	X	X
Pulmonary function test (spirometry) (60)		X	X		X	X	X	X
Concomitant medications	X	X	X	X	X	X	X	X
Adverse events (61)		X	X	X	X	X	X	X
Biomarkers								
Urine: NNAL, Acrylonitrile (CYMA) Acrolein (3-HPMA) (20, 62, 63)			X			X		X
Pregnancy test	X		X			X		X

Procedures during COVID-19:

Remote Visit 1 (Week -3)

Remote Visit 1 will occur over Zoom or the telephone. During Remote Visit 1, participants will be screened using Screener 2. If the participant meets eligibility using Screener 2 the following information will be collected over Zoom or the telephone to determine eligibility in accordance with inclusion/exclusion criteria mentioned above:

1. NIDA Drug Screener
2. Obtain medical and concomitant medication histories
3. Administer all modules in the Mini International Neuropsychiatric Interview (MINI) and current suicide risk assessment (see MINI Standard (version 7.0.2) document). Researchers will administer the MINI mental health diagnostic tool electronically through the nView Health online application. **Procedure for suicide risk at screening:** If a participant scores ≥ 9 on the MINI suicide module the Psychiatric Medical Monitor ([name]) will be contacted. The researcher will discuss the score with the Psychiatric Medical Monitor and they will determine if the participant's enrollment into study is appropriate.

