ask about the number of e-cig uses, number of cigarettes smoked, and any non-study cigarettes smoked. During the first week of the online survey, participants will also be asked about nicotine withdrawal symptoms. If participants do not have a reliable cell phone and internet access they will complete the information on paper logs.

Phone Call (Week 1)

Study staff will call participants to check in on their use of the study cigarettes/e-cig, remind them to use the study products, document any adverse events, and remind them to fill out their e-cigarette and cigarette use log on paper and through the online surveys. If any data on the e-cigarette and cigarette use log online survey is missing it will be collected over the phone with the participant.

Visit 4-7 (Weeks 4, 8, 12, 16)

Participants will return their e-cig and cigarette use log, and have a comprehensive set of measures recorded according to the visit (Table 1). Measures will be completed electronically on a participant computer via REDCap or administered by a study coordinator. Participants will be given a laptop with access only to the internet and an individualized REDCap survey will be opened so they can complete direct data entry. Women of child bearing potential will be retested for pregnancy at Visits 5 and 7.

The study staff will give participants e-cig and cigarette use logs and instruct them to record daily use at each visit. All participants will be asked about their use of other nicotine/tobacco products and if they vaped/smoked any other substances other than nicotine/tobacco at each visit as this could affect the urine biomarkers collected during the study (e.g. carbon monoxide and cotinine levels). Participants will be encouraged/provided advice to substitute some of their cigarettes with their e-cigarette.

Participants will receive a 4-week supply of research cigarettes (130% of daily consumption) and e-liquid pods to last approximately 28 days until the next appointment. Participants will be asked to return all opened, unopened and empty cigarette packs and all used/unused e-liquid pods to the study center at each visit in order to monitor use.

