At Visit 7, participants will return all used and unused research cigarette packs. No more cigarettes will be given. Participants will be allowed to keep their e-cig and unused e-liquid pods until the next visit. Participants will return their e-cig and cigarette use logs. Urine samples for biomarkers will be taken. Participants will complete all biomeasures and questionnaires outlined in Table 1. Participants will be advised to quit smoking completely and provided with the quitline number and sources of free/low cost nicotine replacement therapy (NRT) (see Cigarette Smoking Cessation Tools handout document). The Surgeon General booklet will also be given (see the Consumer Surgeon General Report Booklet document). Participants will be asked about their plans to either (a) go back to their own cigarettes only (b) go back to own cigarettes but supplement with an e-cig, (c) continue using an e-cig only, or (d) quit tobacco/e-cigs completely. Participants will be compensated for completing the study visit and procedures.

A study pulmonologist was added to the study team. We will be monitoring lung function using pulmonary function testing that will be completed at Visits 4-7. Any significant worsening (10% worsening or greater) in pulmonary function will be documented as an adverse event. These adverse events will be reviewed by the Safety Monitors in a timely manner. In cases where the Safety Monitor suspects that a participant may be having a respiratory adverse event related to

the study product, a study pulmonologist will be consulted. The pulmonologist will make any needed medical recommendations and a determination regarding whether the participant is able to continue with the study. For more urgent and/or serious adverse events, the Safety Monitor and/or the study pulmonologist will be consulted and immediate medical attention will be sought if needed.

Procedures during COVID-19:

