Visits 3-5 and 7 will be completed in-person. Participants will be screened for COVID-related symptoms using a modified version of the Patient Screening Questions from the Penn State Health website. Remote Visit 6 will be completed remotely over Zoom or the telephone. Questionnaires for visits outlined in Revised Table 1 will be sent to the participant via a survey link before the in-person visit. Participants will be encouraged to complete the questionnaires 2 hours before the visit, but will have up to 24 hours to complete them after the visit. Participants will return their e-cig and cigarette use log. Biomeasures will be taken as outlined in Revised Table 1. No biomeasures will be collected at Remote Visit 6. Women of child bearing potential will be retested for pregnancy at Visits 5 and 7.

The study staff will give participants e-cig and cigarette use logs and instruct them to record daily use at each visit. All participants will be asked about their use of other nicotine/tobacco products and if they vaped/smoked any other substances other than nicotine/tobacco at each visit as this could affect the urine biomarkers collected during the study (e.g. carbon monoxide and cotinine levels). Participants will be encouraged/provided advice to substitute some of their cigarettes with their e-cigarette.

Participants will receive a 4-week supply of research cigarettes (130% of daily consumption) and e-liquid pods to last approximately 28 days until the next appointment. At Visit 5, participants will receive an 8-week supply of e-cigarettes and cigarettes due to Remote Visit 6 being a remote visit. Participants will be asked to return all opened, unopened and empty cigarette packs and all used/unused e-liquid pods to the study center at each visit in order to monitor use.

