At Visit 7, participants will return all used and unused research cigarette packs. No more cigarettes will be given. Participants will be allowed to keep their e-cig and unused e-liquid pods until the next visit. Participants will return their e-cig and cigarette use logs. Urine samples for biomarkers will be taken. Participants will complete all biomeasures and questionnaires outlined in Revised Table 1. Participants will be advised to quit smoking completely and provided with the quitline number and sources of free/low cost nicotine replacement therapy (NRT) (see Cigarette Smoking Cessation Tools handout document). The Surgeon General booklet will also be given (see the Consumer Surgeon General Report Booklet document). Participants will be asked about their plans to either (a) go back to their own cigarettes only (b) go back to own cigarettes but supplement with an e-cig, (c) continue using an e-cig only, or (d) quit tobacco/e-cigs completely. Participants will be compensated for completing the study visit and procedures.

A study pulmonologist was added to the study team. We will be monitoring lung function using pulmonary function testing that will be completed at Visits 4, 5, 7. Any significant worsening (10% worsening or greater) in pulmonary function will be documented as an adverse event. These adverse events will be reviewed by the Safety Monitors in a timely manner. In cases where the Safety Monitor suspects that a participant may be having a respiratory adverse event related to the study product, a study pulmonologist will be consulted. The pulmonologist will make any needed medical recommendations and a determination regarding whether the

participant is able to continue with the study. For more urgent and/or serious adverse events, the Safety Monitor and/or the study pulmonologist will be consulted and immediate medical attention will be sought if needed.

Follow-up Visit 8 (Week 20)

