8.3 Statistical methods

Basic baseline statistics including means (standard deviations) and frequency distributions (percentages) will be reported for demographic characteristics, smoking characteristics, nicotine dependence, and nicotine and toxicant exposure. Characteristics will be reported by the four treatment arms to identify treatment arm imbalances. Numerical baseline characteristics will be compared among four arms using ANOVA tests or nonparametric Kruskal-Wallis tests when appropriate. Categorical variables will be compared using chi-square tests or Fisher's exact tests. The focus of the statistical analysis will be the difference between four trial arms in terms of the biomarkers of toxicity and health effects. Analyses will be conducted in two approaches, which will address our research questions in two different angles. The first approach is a simplified and streamlined one, the longitudinal measurements of these biomarkers over the 16-week period will be summarized by using just the baseline (visit 3, pre-randomization) and final (visit 7, end of randomization period) measurements. Analysis of Covariance (ANCOVA) models will be used to compare the final measurements among the four arms, while the baseline measurements will be treated as controlled covariates in the model. Specifically, the comparisons between arms 1 and 3 and between arms 2 and 4 answer whether switching to very low nicotine cigarettes leads to lower markers of harm as compared to continuing on normal nicotine cigarettes. This addresses specific Aim 1. Furthermore, we will study if this reduction is the same when combined with 5% nicotine e-cigs (arms 1 and 3) and combined with placebo e-cigs (arms 2 and 4). Similarly, comparison between arm 1 and arm 2 reveals if access to nicotine versus placebo e-cigs impacts these biomarkers. This will address Aim 2. In particular, we will test if the arm 3 has the best outcome as stipulated in Aim 2. These analyses will be conducted using ANCOVA models with interaction terms between traditional cigarettes (normal nicotine vs. very low nicotine) and e-cig (5% vs. 0%). Appropriate transformation may be done on some of the outcome variables (for example log-transformation) to make sure the underlying statistical assumptions are all satisfied. Note that for NNAL, one of our main biomarkers of toxicity; it can only be analyzed using the first approach due to the limitation of number of measures.

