The second approach for biomarker analysis will use the longitudinal data analysis to model all the repeated measurements of these biomarkers over the entire 16 weeks. Their trajectories will be plotted for each of the 4 arms. Linear mixed-effect models will be used to model the biomarker measurements on the following predictors: time after randomization (X1, which can be measured in weeks (continuous or visit number (categorical))), normal vs. low nicotine cigarettes (X2), 5% nicotine e-cig vs. placebo e-cig (X3), the interaction between cigarette and e-cig (X2*X3), and the interaction between X1 and X2, X3, X2*X3. In particular, the three-way interaction of X1, X2 and X3 indicates an interaction between cigarette type (NNC versus VLNC) and e-cig type (nicotine versus placebo) on their effect on the change of these markers of harms to health over time. Note that the time variable (X1) can be treated as either categorical or continuous, which will lead to different statistical models – growth curve model vs repeated-measure ANOVA models. If X1 is treated as categorical, then the estimated means and 95% confidence interval (CI) values of the outcome variables will be reported using tables. If X1 is treated as continuous, then the point estimates and 95% CI of the coefficients (rate of changes) will be reported. The baseline (before randomization) measures of the outcome variables will be included in the model as a controlled covariate. Family-wise type-I error rate due to multiple comparisons will be controlled at the visit level (if X1 is treated as categorical) using Bonferroni method. Again, appropriate transformation of the outcome variable may be carried out – similar to the first approach.

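### NNAL is limited to a week 0/week 16 ANCOVA for lack of measures, yet both visit schedules mark a week-8 urine NNAL sample

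*Combined protocol and SAP*

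**What the plan says.** Section 1.2 makes urinary NNAL at week 16 the primary endpoint. Section 8.3 describes two analyses of the biomarkers. The first is an ANCOVA of the Visit 7 value with the Visit 3 value as covariate. The second is a linear mixed model on all repeated measurements, with time either categorical or continuous; in it, "The baseline (before randomization) measures of the outcome variables will be included in the model as a controlled covariate". For NNAL the section then says "it can only be analyzed using the first approach due to the limitation of number of measures".

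The schedules in section 7.2 carry a row headed "Urine: NNAL, Acrylonitrile (CYMA) Acrolein (3-HPMA) (20, 62, 63" with three marks in Table 1 and three in Revised Table 1. The visit narrative mentions biomarker urine at Visit 3 and again at Visit 7 ("Urine samples for biomarkers will be taken"), but not at Visit 5. For Visits 4 to 7 it says that participants "have a comprehensive set of measures recorded according to the visit (Table 1", so the table governs.

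Section 8.3 adopts the intention-to-treat principle but gives no method for a missing week-16 value. Section 3.3.2 provides limited recontact: for those lost to follow-up, "one final attempt will be made to contact them for the week 16 visit via one call, message and letter". Participants who withdraw and decline contact are not approached.

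**The concern.** The documents disagree on whether a week-8 NNAL value will exist for the primary endpoint. Site staff following the tables would collect it; a statistician following section 8.3 would plan without it. CYMA and 3-HPMA share the NNAL row and its three time points, yet the restriction names NNAL alone.

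The consequence lies in missing data. A two-point ANCOVA uses only participants with a week-16 sample. If loss after week 8 is related to the week-8 value, the completers in an arm are a selected group and the arm difference can be biased in either direction. The documents do not allow one to predict which. A model that includes week 8 removes the part of that bias that the week-8 value explains.

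**Working it through.** **1. The plan's own figure.** Section 8.2 gives 60 per arm for 80% power, effect 0.58 SD, alpha 0.05/3 (printed as 0.017), two-sided. With n = 2(z₁₋α/₂ + z₀.₈)²/d²: 2 × (2.387 + 0.842)²/0.58² = 62 per arm. At 60 per arm, power is 0.785 at alpha 0.017. The figure reproduces approximately and does not depend on week 8.

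**2. Which visits the urine row marks.** The column order is Visits 1, 2, 3, phone call, 4, 5, 6, 7 and, in Revised Table 1, 8. In both tables the urine marks fall in columns 3, 6 and 8, which are Visits 3, 5 and 7 (weeks 0, 8 and 16). Because table text can shift on extraction, each table was checked against another row:

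- Table 1: the pregnancy-test row uses the same three columns (plus Visit 1), and the narrative places the retests at Visits 5 and 7.
- Revised Table 1: the pregnancy row is visibly shifted and is not relied on. The spirometry row marks Visits 2, 3, 4, 5 and 7, which agrees with the narrative ("pulmonary function testing that will be completed at Visits 4, 5, 7"). Its last two marks share columns with the last two urine marks.
- Visit 5 stays on site under the COVID-19 procedures: "Visits 3-5 and 7 will be completed in-person".

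**3. Can the second approach be fitted?** With baseline as covariate, weeks 8 and 16 leave two outcome values per person. On one simulated data set of 240 participants the categorical-time mixed model converged. Its week-16 cigarette effect in the placebo e-cig arms was -0.384 + (-0.007) = -0.391, and the week-16 ANCOVA gave -0.391. With complete data the two agree.

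**4. Precision under random loss.** Let d8 and d16 be cumulative loss by weeks 8 and 16, and r the week 8/week 16 correlation given baseline. The variance of the week-16 contrast, mixed model over ANCOVA, is 1 - r²[1 - (1 - d16)/(1 - d8)]. For d8 = 0.10, d16 = 0.20, r = 0.7: 1 - 0.49 × (1 - 0.80/0.90) = 0.946. Power uses alpha 0.05/3; loss rates and r are assumptions.

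| Loss by week 8 / 16 | Variance ratio, r = 0.5 to 0.8 | Power, ANCOVA | Power, with week 8 |
|---|---|---|---|
| 0 / 0 | 1.00 | 0.783 | 0.783 |
| 10% / 20% | 0.97 to 0.93 | 0.673 | 0.687 to 0.710 |
| 10% / 30% | 0.94 to 0.86 | 0.604 | 0.633 to 0.683 |
| 15% / 40% | 0.93 to 0.81 | 0.527 | 0.565 to 0.632 |

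**5. Bias when loss depends on week-8 NNAL.** From section 8.2: difference log(0.78) = -0.248, SD 0.562, 60 per arm. Assumed: all loss after week 8, 15 to 25%; logistic dropout with slope 1.5 per SD of week-8 log NNAL; baseline correlation 0.5 with week 8/week 16 correlation 0.7, or 0.6 with 0.8. Contrast: arm 3 against arm 1; 2,000 replicates per scenario.

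| Who is lost | ANCOVA, range | ANCOVA, 0.5/0.7 and 25% | Week-8 model, same setting |
|---|---|---|---|
| High NNAL, VLNC only | -0.29 to -0.32 | -0.316 | -0.245 |
| High NNAL, both | -0.22 to -0.23 | -0.221 | -0.244 |
| High NNAL, NNC only | -0.18 to -0.21 | -0.179 | -0.251 |
| Low NNAL, VLNC only | -0.17 to -0.21 | -0.171 | -0.243 |
| Random | no bias | -0.246 (SE 0.1016) | -0.246 (SE 0.0953) |

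The largest errors are (0.316 - 0.248)/0.248 = 27% away from zero and (0.248 - 0.171)/0.248 = 31% toward zero. At the planned effect, 0.58 × 0.562 = 0.326, the ANCOVA runs from about -0.40 to -0.26 and the week-8 model stays at -0.32 to -0.33.

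**The case against.** The planned ANCOVA is a valid estimator of the stated endpoint. With complete data week 8 adds nothing, and under random loss there is no bias to remove. Collection is also not assay: urine is banked (section 20.1), and the narrative names biomarker urine only at Visits 3 and 7, so two assays may have been intended. The stated reason is fair for a random-slope growth curve, which two post-baseline points would support only weakly. All of this stands. It narrows the criticism to the categorical-time model and makes the remedy depend on whether week 8 is assayed.

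The bias figures also favour the week-8 model. Loss is placed wholly after week 8 and driven by the observed week-8 value, so that model is unbiased by construction, and a slope of 1.5 per SD is strong. In two-arm checks with VLNC-only selection at correlations 0.5/0.7, a slope of 0.5 gives an ANCOVA estimate of -0.263 at 15% loss and -0.279 at 25%, against a true -0.248. With slope 1.5 and 25% loss, if half of those lost leave before week 8, the week-8 model gives -0.275. If the unseen week-16 value drives the loss, it gives -0.328 and the ANCOVA -0.368. So the gain may be smaller than tabulated, and the mixed model is not a cure for every mechanism. In the last case both fail, the ANCOVA by more.

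Leaving an intermediate value unused is not itself a breach of intention to treat. The real gap is the missing-data rule, and that remains.

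**Conclusion.** The concern holds. The schedules mark three NNAL samples, section 8.3 plans as if there were two, and nothing in the documents says the week-8 sample is not assayed. If it is assayed, lack of measures is no reason to exclude the categorical-time mixed model.

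The size is moderate and conditional: no effect with complete data; a standard error 2 to 7% smaller under random loss in the simulations; and up to about 30% bias in either direction for the ANCOVA if loss after week 8 depends strongly on week-8 NNAL in one arm. The loss rates, correlations and dropout mechanisms are assumptions, because the documents state none. The 300-to-240 allowance in section 8.1 covers loss before randomisation only. The advantage of the week-8 model rests on missing at random given the observed values. This should be corrected; it does not invalidate the trial.

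**What to change.** First, reconcile Table 1, Revised Table 1, the narrative for Visits 4 to 7 and section 8.3 on whether week-8 urine is assayed for NNAL.

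- **If it is:** delete the restriction. Make the primary analysis a repeated-measures mixed model on log NNAL at weeks 8 and 16, with categorical visit, cigarette type, e-cig type, their interactions with each other and with visit, baseline log NNAL by visit, and unstructured covariance. Keep the week-16 contrast as the primary estimate; averaging weeks 8 and 16 would change the endpoint. Keep the two-point ANCOVA as a sensitivity analysis.
- **If it is not:** correct the urine row in both tables and state how a missing week-16 NNAL value is handled in the ANCOVA.

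In either case, state the missing-at-random assumption and that participants with no post-baseline sample contribute nothing to the estimate.

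The cost is small. With assays already planned, it is SAP wording and a few lines of code. Without them, it is two table rows and a sentence on missing data.

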1.2 Primary Study Endpoints

The primary endpoint for the study is urinary NNAL concentration at Week 16. Urine NNAL is a biomarker that provides an accurate estimate of recent exposure to the lung carcinogen, NNK.

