2.2 Previous Data

Below, we summarize key relevant findings from our team’s recent research, which leads to both our interest and expertise in conducting this proposed study.

Research on Reduced Nicotine Content Cigarettes. In our recently completed trial, participants were randomly assigned to smoke either (a) NNC cigarettes (11.6 mg/cig); or b) Reduced Nicotine Content (RNC) cigarettes where the nicotine content per cigarette is progressively reduced to 0.2 mg/cig in five steps over 18 weeks. Participants were then offered the choice to either (a) quit smoking with assistance, (b) continue smoking the research cigarettes, or (c) return to their own cigarettes, and were followed up for a further 12 weeks. After controlling for the baseline measure, plasma cotinine, exhaled CO and FTND score were all significantly lower at the end of randomized phase in the RNC group as

compared to the NNC group. Measures of nicotine dependence (mean cigarettes smoked per day, Penn State Cigarette Dependence Index) were significantly lower at the end of the randomized phase in the RNC group, as compared to the NNC group ($p<0.003$), whereas measures of psychiatric problems (CES-D depression score, QIDS depression score, OASIS anxiety score and MNWS nicotine withdrawal score) showed no significant change in the RNC group as compared to the NNC group. Analyses focusing on those participants who were compliant with exclusive use of research cigarettes throughout the randomized phase of the trial (in the RNC group having a reduction in mean cotinine from 245 ng/ml at visit 4 to 8 ng/ml at visit 10), found an almost identical pattern of results to the randomized phase completer analysis.

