Intent-to-treat (ITT) principle will be adopted for the analyses in both approaches. Additionally, the measurements of tobacco use and addiction and measurements of mental health will be monitored and summarized, and will be compared across these arms in a similar statistical fashion as described above. Self-reported compliance will be reported for all participants. For participants in arm 4 (VLNC plus placebo ecigs) their compliances will be further evaluated using biomarkers. Comparison on the outcome variables will be made between compliers vs non-compliers within arm 4 participants only. All analyses will be conducted using statistical software SAS version 9.4 or higher (SAS Institute, Cary, NC, USA) and R Programming language version 3.6.1 or higher (R Foundations). All tests will be two-sided and the statistical significance level to be used is 0.05.

Adjusted models will evaluate the treatment effect while adjusting for covariates, such as gender, age, race, SDOH scoring, and other baseline factors.

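### ITT is declared, but the primary NNAL ANCOVA keeps only participants with a week-16 urine, and no rule covers the rest

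*Combined protocol and SAP*

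**What the plan says.** - Section 1.2: "The primary endpoint for the study is urinary NNAL concentration at Week 16".
- Section 8.3, first approach: "Analysis of Covariance (ANCOVA) models will be used to compare the final measurements among the four arms", with the visit 3 value as covariate. The second approach is a mixed model on repeated measures, but NNAL is kept out of it: "it can only be analyzed using the first approach due to the limitation of number of measures".
- Section 8.3, on the analysis principle: "Intent-to-treat (ITT) principle will be adopted for the analyses in both approaches". No analysis set, missing-data method or sensitivity analysis follows.
- Section 3.3.2, for those who withdraw themselves: "For participants who withdraw themselves from the study, they will be asked if we can follow up with them at the week 16 visit". For those lost to follow-up: "one final attempt will be made to contact them for the week 16 visit via one call, message and letter". Participants withdrawn at a visit are asked to complete that visit. No week-16 step is given for those the investigator withdraws.
- Section 3.3.1: the investigator's grounds for withdrawal include more than a doubling of cigarettes per day together with a large rise in exhaled CO.
- Section 7.2: when an in-person visit is missed, staff try to collect data by phone.
- Table 1 and Revised Table 1 (section 7.2): the urine biomarker row has three marks. In Table 1 they line up with the pregnancy-test marks that the text places at visits 5 and 7, so they read as weeks 0, 8 and 16.

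**The concern.** An ANCOVA on the week-16 value cannot use a participant who has none. With the mixed model ruled out for NNAL and nothing else specified, such participants disappear from the primary analysis while the result carries the ITT label.

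The loss may not be neutral. VLNC cigarettes come from the study, so a participant who leaves a VLNC arm and goes on smoking is likely to return to normal-nicotine cigarettes. In that person the effect of allocation at week 16 is close to zero. Leaving the person out removes a near-zero contribution from the average, and the estimated benefit grows. The investigator-withdrawal rule in section 3.3.1 also removes people for a rise in smoking, which is closely tied to the endpoint, and a phone contact yields no urine.

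At stake are the Aim 1 contrasts, arm 1 v arm 3 and arm 2 v arm 4. The reported effect would lean towards those who stayed, yet be read as the effect of allocation in all 240 randomised.

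**Working it through.** **1. The plan's own figure.** Inputs from section 8.2: 60 per arm, effect 0.58 SD, alpha 0.05/3; tests are two-sided (section 8.3). Power = Φ(0.58/√(2/60) − 2.394) = Φ(3.177 − 2.394) = 78.3%, close to the stated 80%. This holds only if all 60 in each arm give a week-16 value. The step from 300 enrolled to 240 randomised (section 8.1) is loss before randomisation; nothing is allowed for loss after it.

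**2. Effect of losing leavers, VLNC v normal nicotine.** The documents give no post-randomisation loss, reversion or retrieval rate, so all of these are assumed. Let d be the share of the VLNC arm that leaves, r the share of leavers who still give a week-16 urine, and 0.58 SD the effect in those who stay. Suppose that leavers sit at the normal-nicotine level and that loss from the comparator arm is neutral.

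- Effect in all randomised = 0.58 × (1 − d).
- Effect in those observed = 0.58 × (1 − d)/(1 − d + rd).
- Ratio, observed to all randomised = 1/(1 − d + rd).

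| Loss d | All randomised (SD) | Observed, r = 0 (SD) | Ratio, r = 0 | Observed, r = 0.5 (SD) | Ratio, r = 0.5 |
|---|---|---|---|---|---|
| 10% | 0.522 | 0.58 | 1.11 | 0.549 | 1.05 |
| 20% | 0.464 | 0.58 | 1.25 | 0.516 | 1.11 |
| 30% | 0.406 | 0.58 | 1.43 | 0.478 | 1.18 |

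With full retrieval the ratio is 1.00. Taking the plan's SD of 0.562 for log NNAL at face value, the geometric mean ratio among stayers is exp(−0.58 × 0.562) = 0.722. In all randomised it is 0.746, 0.770 or 0.796 at 10%, 20% or 30% loss.

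A simulation of the ANCOVA (4,000 trials, 60 per arm, assumed baseline correlation 0.6, 20% loss in each arm) agrees: −0.582 observed v −0.467 in all randomised with no retrieval, and −0.540 v −0.465 with 30% retrieved.

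**3. Arm 3 v arm 4.** Both are VLNC arms, so the direction depends on the loss in each. Assume a VLNC effect of 0.45 SD, an e-cig effect of 0.13 SD, and loss of 20% in arm 3 and 35% in arm 4. The contrast in stayers is 0.13. In all randomised it is 0.80 × 0.58 − 0.65 × 0.45 = 0.464 − 0.2925 = 0.17. Here the available-case result understates.

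**4. What a remedy must do.** Within-arm imputation gives leavers the values expected of stayers with similar histories. In simulation with 20% loss and reversion it left the estimate at −0.58 against a true −0.47. Imputing missing VLNC values from the normal-nicotine arm gave −0.46, in line with 0.58 × 0.80 = 0.464. Where leaving depended on the week-8 NNAL, imputation using that value moved a bias of −0.06 to about 0. The two tools address different mechanisms, so both are needed.

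**The case against.** The strongest reply is section 3.3.2. The plan seeks week-16 visits from participants who withdraw themselves and from those lost, which retrieves off-product outcomes as ITT requires. A reader might infer that the primary analysis is a completer analysis. The documents do not support that: retrieved leavers and non-compliers who still attend are included. Retrieval is limited, though. It is one call, message and letter, those who decline contact are left alone, and investigator-withdrawn participants are not covered.

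Section 2.2 may tempt the same inference, since compliant participants in the sponsor's earlier trial "found an almost identical pattern of results to the randomized phase completer analysis". But that section also reports quitting by intent to treat in all 188 randomised, and neither statement fixes how NNAL will be handled here.

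Full reversion is also a worst case. Leavers may quit or use only e-cigs, both of which section 7.2 lists as plans at visit 7. Someone who simply misses visit 7 may still hold study cigarettes, because supplies run at 130% of consumption. This stands, and the percentages are conditional on it.

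Finally, a reader might infer that the test would reject too often when there is no effect. That needs leaving to depend on the unobserved week-16 value, and by an amount the documents do not give. If leaving depends on baseline NNAL, the ANCOVA covariate adjusts for it.

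**Conclusion.** The concern holds as a gap between the declared principle and the specified model. ITT is stated, but the primary NNAL analysis is available-case by default. Its likely consequence for the VLNC v normal-nicotine contrasts is overstatement: 11% to 43% for 10% to 30% loss with no retrieval, and about 5% to 18% with half of leavers retrieved. These figures rest on assumed loss and retrieval rates, and on unretrieved VLNC leavers returning to the normal-nicotine level. With full retrieval the bias vanishes. No direction can be claimed for arm 3 v arm 4, and no inflated false-rejection rate is established. The point should be settled before unblinding.

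**What to change.** In section 8.3:

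- Define the primary NNAL set as all 240 randomised, by assigned arm, including off-product week-16 values retrieved under section 3.3.2.
- Handle missing week-16 log NNAL by a mixed model or by multiple imputation within arm. Use baseline NNAL, the week-8 NNAL, on-study cigarettes per day, and CO where it exists. CO is absent at remote visit 6 and during the COVID pause.
- Confirm that NNAL is sampled at week 8 and, if so, correct the statement that it has too few measures for anything but the first approach.
- Because neither the mixed model nor within-arm imputation corrects for reversion, pre-specify a reference-based sensitivity analysis: missing values in arm 3 imputed from arm 1, and in arm 4 from arm 2.
- Report the available-case ANCOVA as supportive.

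In section 3.3.2, extend the week-16 urine request, with consent, to participants withdrawn by the investigator. This asks only for a sample and leaves the withdrawal criteria unchanged.

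The cost is SAP wording, modest programming and some extra contacts and samples. The reported effect may be smaller than among those observed.
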